5. SCHEDULE OF EVENTS

NOTE: Observation visits ([Table 2](#)) in the open-label extension study begin after completion of double-blind study (Day 71). Treatment sessions ([Table 3](#)), if elected, will begin after study drug blind is broken in study EN3835-201 while observation visits continue concurrently.

Table 2: Observation Assessments

Procedures	Screening A ^a (≥Day 71 Visit of Double-blind Study)	Visit 1 Day 90 ^b (±7 days)	Visit 2 Day 180 ^b (±7 days)	Visit 3 Day 270 ^b (±7 days)	Visit 4 End of Study/ Early Termination Day 360 ^{b,f} (±7 days)
Informed Consent	X				
Inclusion/Exclusion	X				
Digital photography		X ^c	X ^c	X ^c	X ^c
Prior/Concomitant Medications/Procedures	X	X	X	X	X
Body weight		X	X	X	X
Vital signs		X	X	X	X
Collection of samples:					
• Clinical laboratory					X
• Anti-AUX-I/anti-AUX-II antibody level					X
Subject cellulite assessments:					
• Patient Reported Photounumeric Cellulite Severity Scale (PR-PCSS)		X ^{d,e}	X ^{d,e}	X ^{d,e}	X ^{d,e}
• Subject Global Aesthetic Improvement (S-GAIS)					X ^{d,e}
• Subject satisfaction with cellulite treatment assessment					X ^{d,e}
Investigator cellulite assessments:					
• Clinician Reported Photounumeric Cellulite Severity Scale (CR-PCSS)		X ^e	X ^e	X ^e	X ^e
• Hexsel Cellulite Severity Scale (CSS)					X ^e
• Investigator Global Aesthetic Improvement (I-GAIS)					X ^e
Injection site reactions/local tolerability in assigned quadrant from EN3835-201 study		X	X	X	X
Adverse events		Monitored Throughout Study			

^a Informed consent for open-label observation assessments and optional treatment election.

^b Four (4) visits at 3-month periods begin 90 days after Day 1 of the double-blind study (EN3835-201) (ie, within 20 days ± 4 days of completion of double-blind study).

^c Only the treated quadrant(s) is photographed. For subjects participating in observation-only visits, the quadrant treated in the double-blind study (EN3835-201) is photographed; for subjects with open-label treatment (treated with EN3835 in study EN3835-202), the treated quadrant is photographed.

^d Assessment made via viewing digital image photograph.

^e Assessment of treated quadrant(s) only.

^f For subjects treated with active EN3835 in the double-blind study and having a different quadrant treated in the open-label study, refer to Table 4 for continued assessments of the double-blind treated quadrant for durability beyond Day 360.

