NOTE: Subject cellulite assessments must be completed before the Investigator cellulite assessments are conducted at each visit.

Table 3: Treatment Session Assessments

Procedures	Screening B ^a (Day -14 to -1 relative to Tx Visit 1)	Tx Visit 1 Tx Session 1 Day 1	Tx Visit 2 Tx Session 2 Day 22 (± 3 days)	Tx Visit 3 Tx Session 3 Day 43 (± 3 days)	Tx Visit 4 End of Treatment/ Early Termination Day 71 (± 5 days) ^b
Inclusion/Exclusion	X				
Digital photography	X ^c	X ^{c,d}	X ^{c,d}	X ^{c,d}	X ^c
Medical history/EFP history including previous treatments	X ^{k,m}				
Prior/Concomitant Medications/Procedures	X ^{k,m}	X ^m	X	X	X
Physical examination:	X				
• Body weight	X ^m		X ^e	X ^e	X
• Height	X ^m				
Vital signs	X	X ^f	X ^f	X ^f	X
12-lead ECG	X ^l				
Collection of samples:					
• Clinical laboratory	X ^m				X
• Anti-AUX-I/anti-AUX-II antibody level		X ^{e,m}			X
• Urine pregnancy testing	X	X ^e	X ^e	X ^e	
Subject cellulite assessments:					
• Patient Reported Photometric Cellulite Severity Scale (PR-PCSS)	X ^{g,h}		X ^{e,g,h}	X ^{e,g,h}	X ^{g,h}
• Subject Global Aesthetic Improvement (S-GAIS)					X ^{g,h}
• Subject satisfaction with cellulite treatment assessment					X ^{g,h}
Investigator cellulite assessments:					
• Selection of dimples to be treated within selected quadrant		X ^e	X ^e	X ^e	
• Marking the dimples to be treated within selected quadrant		X ^e	X ^e	X ^e	
• Clinician Reported Photometric Cellulite Severity Scale (CR-PCSS)	X ^h		X ^{e,h}	X ^{e,h}	X ^h
• Hexsel Cellulite Severity Scale (CSS)	X ^{h,i}				X ^h
• Investigator Global Aesthetic Improvement (I-GAIS)					X ^h
Confirm Eligibility	X	X ^e			
Select Quadrant	X ^j				
Study drug administration		X	X	X	
Injection site reactions/local tolerability in selected quadrant		X	X	X	X
Adverse events					Monitored Throughout Study

EN3835-202 Protocol Amendment 4

^a After the study drug blind is broken in study EN3835-201, eligible subjects may elect to receive EN3835 treatments.

^b Upon completion of treatment, subject will be followed at 3-month intervals as in [Table 2](#); if study terminates early, subject will be followed through Visit 4 (Day 71). If subject received placebo in the double-blind study (EN3835-201), she may be eligible for a total of 2 courses of treatment (a total of 6 treatment sessions) in this study.

^c All 4 quadrants are photographed at screening; at other visits, the selected quadrant only is photographed.

^d Before and after marking the dimples.

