7. LIST OF ABBREVIATIONS

The following abbreviations and specialist terms are used in this study protocol.

Table 5: Abbreviations and Specialist Terms

Abbreviation	Definition
AE	Adverse event
Assigned quadrant	Assigned quadrant (ie, left or right buttock, or the left or right posterolateral thigh) that was suitable for treatment and was randomly assigned in the double-blind study (EN3835-201). To be suitable for treatment the quadrant must have an Investigator CR-PCSS and subject PR-PCSS score of 3 or 4 and a Hexsel CSS score of no greater than 13 at Screening B visit and at Day 1 visit.
AUX-I	Clostridial class I collagenase
AUX-II	Clostridial class II collagenase
CFR	Code of Federal Regulations
CRF	Case report form
CR-PCSS	Clinician-Reported Photometric Cellulite Severity Scale
CSS	Cellulite Severity Scale
ECG	Electrocardiogram
eCRF	Electronic case report form
EDC	Electronic data capture
EFP	Edematous fibrosclerotic panniculopathy
FDA	Food and Drug Administration
GCP	Good clinical practice
HREC	Human research ethics committee
IB	Investigator Brochure
ICF	Informed consent form
ICH	International Conference on Harmonisation
IEC	Independent ethics committee
I-GAIS	Investigator Global Aesthetic Improvement Scale
IND	Investigational new drug
IRB	Institutional review board
ITT	Intent-to-treat
kDa	Kilodalton
MedDRA	Medical Dictionary for Regulatory Activities
mITT	Modified intent-to-treat
PCS	Potentially clinically significant
PR-PCSS	Patient-Reported Photometric Cellulite Severity Scale
Qualified designee	Qualified by education and training to perform the study procedure (eg, sub-Investigator, nurse)

Table 5: Abbreviations and Specialist Terms (Continued)

Abbreviation	Definition
SAE	Serious adverse event
SAP	Statistical Analysis Plan
Selected quadrant	Quadrant (ie, left or right buttock, or the left or right posterolateral thigh) that is suitable for treatment and is selected by patient and investigator for treatment. To be suitable for treatment the quadrant must have an Investigator CR-PCSS and subject PR-PCSS score of at least 3 or 4 and a Hexsel CSS score of no greater than 13 at Screening B visit.
S-GAIS	Subject Global Aesthetic Improvement Scale
TEAE	Treatment-emergent adverse event; adverse events that occur on or after the first injection of study drug

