12.1.3.1. Three-Month Assessments

Subjects will return within 20 days (± 4 days) of completion of the double-blind study for the first of 4 safety and cellulite severity evaluation visits. Assessments to be completed at these visits are detailed in Table 2. Subjects are to return at 3-month intervals until they have completed at least 12 months from Day 1 of the double-blind study. At these visits, the quadrant previously treated with EN3835 in the EN3835-201 study or quadrants treated with EN3835 in the

open-label study will be evaluated. If the quadrant treated in study EN3835-201 is retreated in the open-label study, the 3-month assessments will reset to treatment visit 1/Day 1 of the open-label treatment and the study visits will continue as described in [Table 3](#) followed by 3-month assessments as described in [Table 2](#). If a different quadrant is treated in the open-label study, the 3-month assessments of both the quadrant treated in the double-blind study (EN3835-201) and the quadrant treated in the open-label study will continue.

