12.1.4.5. Follow-up Visits

Following the Day 71 visit, the quadrant(s) treated with EN3835 in the open label study will be evaluated every 3 months from the first exposure to EN3835 following the schedule in [Table 2](#). The first follow-up visit will be approximately 20 days after the Day 71 visit (ie approximately Day 90 after treatment session 1).

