17.6. Safety Analyses

The following variables are safety endpoints.

- AEs: Mapped to preferred term using the Medical Dictionary for Regulatory Activities (MedDRA)
- Injection site reactions/local tolerability in selected quadrant (through subject and Investigator reporting)
- Vital signs
- Laboratory testing

AEs will be summarized by treatment group. AE duration will be summarized using descriptive statistics by treatment group.

Descriptive statistics will be presented for each clinical laboratory test for the actual and change from screening at each visit by treatment group and vital signs for the actual and change from Day 1 pre-injection for each injection day at each visit by treatment group.

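### Table 2 schedules no local-tolerability check after Day 71 for a quadrant injected in EN3835-202 when it differs from the assigned EN3835-201 quadrant

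*Combined protocol and SAP*

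**What the plan says.** All references are to protocol Amendment 4.

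- **During treatment.** Table 3 schedules "Injection site reactions/local tolerability in selected quadrant" on Days 1, 22, 43 and 71.
- **After Day 71.** Table 3 footnote b states "Upon completion of treatment, subject will be followed at 3-month intervals as in" Table 2. Section 12.1.4.5 agrees: "the quadrant(s) treated with EN3835 in the open label study will be evaluated every 3 months from the first exposure to EN3835", on the Table 2 schedule.
- **Table 2.** Its one tolerability row is "Injection site reactions/local tolerability in assigned quadrant from EN3835-201 study". Section 7 defines the assigned quadrant as the one that "was randomly assigned in the double-blind study (EN3835-201"), and defines the selected quadrant separately as the one chosen for treatment here.
- **What is to be assessed and analysed.** The synopsis (Criteria for evaluation, Safety) promises tolerability in the treated quadrant for subjects treated in this study. Section 17.6 lists as a safety endpoint "Injection site reactions/local tolerability in selected quadrant (through subject and Investigator reporting").
- **Photographs.** Table 2 footnote c opens by limiting photography to the treated quadrant or quadrants, naming no study. It then says that "for subjects with open-label treatment (treated with EN3835 in study EN3835-202), the treated quadrant is photographed". Section 13.1 speaks of photographing the selected quadrant and includes the durability observation visits in its list.
- **Two different quadrants.** Section 12.1.3.1 says that "the 3-month assessments of both the quadrant treated in the double-blind study (EN3835-201) and the quadrant treated in the open-label study will continue". The synopsis says the same.

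**The concern.** The primary objective is long-term safety over 12 months or more. Local tolerability in the injected quadrant is a named safety item. A site that follows Table 2 exactly would stop checking some injected quadrants at Day 71. For a former placebo subject treated only in a new quadrant, it would go on checking the quadrant that had received placebo. The 17.6 endpoint would then have no scheduled data beyond Day 71 for the affected quadrants.

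The photograph wording raises a smaller issue. At Table 2 visits PR-PCSS is rated from the photograph, so a quadrant that is not photographed has no PR-PCSS. If a site read footnote c narrowly, a re-dosed subject's EN3835-201 quadrant would lack the patient-rated half of the 12-month durability record.

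**Working it through.** The plan gives no figure to reproduce. The check sets the schedule against the ways a subject can be treated, and the only arithmetic is on visit days.

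**Step 1. Can the row be shorthand for every treated quadrant?** No. In the same table the cellulite rows carry footnote e, which extends them to the treated quadrant(s). The tolerability row carries no such footnote and names the parent-study quadrant.

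**Step 2. Count the Table 2 visits that schedule tolerability in the EN3835-202 quadrant.**

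| Parent-study arm | Quadrant treated in EN3835-202 | Visits (Days 90, 180, 270, 360) |
|---|---|---|
| Active | Same (re-treatment) | 4 of 4 |
| Active | Different (re-dosing) | 0 of 4 |
| Placebo | Assigned quadrant | 4 of 4 |
| Placebo | Another quadrant | 0 of 4 |
| Placebo | Assigned quadrant, then a different one | 4 of 4 for the first, 0 of 4 for the second |

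Re-dosing subjects fall in a 0-of-4 row by the definition of their cohort in section 17.2.

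**Step 3. Does general adverse event collection fill the gap?** Table 2 says adverse events are monitored throughout. Section 14.5.1 collects them until 30 days after the last dose. The third session is on Day 43 ± 3.

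- Window closes: 43 + 30 = Day 73 (from 40 + 30 = 70 to 46 + 30 = 76).
- Earliest first follow-up visit: 90 − 7 = Day 83.

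Under 14.5.1 the window has closed before the first Table 2 visit. Even where Table 2 governs, section 14.2 elicits events with a general, non-leading question and not a look at a named quadrant.

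**Step 4. Photographs of a re-dosed subject's EN3835-201 quadrant.** The EN3835-202 quadrant is photographed on any reading.

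- Broad reading (footnote c's opening words govern): both quadrants at every visit.
- Narrow reading (only the open-label quadrant once the subject is treated): section 12.1.3 requires former active subjects to complete at least one observation visit before Screening B. At most 4 − 1 = 3 ratings are then lost. If enrolment came after the Day 90 window, the first visit is Day 180 and at most 3 − 1 = 2 are lost.

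Screening B also photographs and rates all four quadrants (Table 3 footnotes c and h), which adds one PR-PCSS on the EN3835-201 quadrant before re-dosing.

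**The case against.** The best defence of the tolerability schedule is that 12.1.4.5 has open-label quadrants evaluated every three months and the synopsis commits to tolerability in the treated quadrant, so a sensible site would check it. In addition, local events in the Phase 1b study settled inside three weeks, so the Day 71 visit should catch most of what is expected. Both points limit the harm, but neither removes the gap. Section 12.1.4.5 defers to Table 2 for what is done, and Table 2 names another quadrant. Late or persistent local effects, which a long-term extension is there to find, are the ones the Day 71 visit cannot show.

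On photographs the defence is stronger. Footnote c begins with a form that allows more than one quadrant. Footnote e has treated quadrant(s) rated. Footnote f speaks of continuing the double-blind quadrant's assessments past Day 360, which presumes they ran until then. Section 12.1.3.1 and the synopsis require both quadrants. What remains is a singular noun in footnote c and the term selected quadrant in 13.1.

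A reader might infer more than the text supports:

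- *Tolerability and photographic data both fail after Day 71 for all open-label subjects.* Treatment confined to the assigned quadrant leaves no gap, and no passage restricts photographs to the EN3835-202 quadrant.
- *The gap is 360 − 71 = 289 days.* Checks occur at visits, and even a corrected table schedules nothing between Day 71 and Day 90. Four visits is the right measure.
- *Four PR-PCSS ratings are lost.* The required observation visit before Screening B caps the loss at three.
- *Re-dosed subjects drop out of the durability population.* Section 17.2.4 asks for both scales at 180 days or later, not at every visit. A rating at Day 180 or later before re-dosing can qualify a subject, as can a Table 4 visit (Days 450 to 720) for an eligible active responder.

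**Conclusion.** The tolerability gap is definite but confined to a subset. When the EN3835-202 quadrant is not the assigned EN3835-201 quadrant, 0 of 4 follow-up visits schedule tolerability in it, contrary to the synopsis and 17.6. The plan does not forecast how many subjects will choose a different quadrant, so the number affected cannot be stated. It includes every re-dosing subject and some former placebo subjects. The conclusion assumes that sites follow Table 2 as written.

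The photograph point is an ambiguity, not an omission. On the narrow reading it puts at most three Table 2 PR-PCSS ratings per re-dosed subject at risk, leaving the 12-month durability record incomplete without by itself excluding anyone. On the broad reading nothing is lost.

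**What to change.** 1. Reword the Table 2 tolerability row to cover each EN3835-treated quadrant, whether treated in EN3835-201 or EN3835-202, and use the same term in 17.6.
2. State in Table 2 footnote c and in section 13.1 that every EN3835-treated quadrant is photographed at the observation visits, in line with 12.1.3.1 and the synopsis.

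The wording should not add follow-up of placebo-injected quadrants, which 12.1.3.1 does not call for. If the sponsor wishes to keep the present check of the assigned quadrant in observation-only former placebo subjects, who belong to the Observational population, that should be stated as an exception. Table 2 and 14.5.1 should also be reconciled on how long adverse events are collected.

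The cost is an edit to one row, one footnote and two sections, plus a local check at visits already scheduled. The photograph and rating of the second quadrant are already implied by 12.1.3.1.

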7. LIST OF ABBREVIATIONS

The following abbreviations and specialist terms are used in this study protocol.

Table 5: Abbreviations and Specialist Terms

Abbreviation	Definition
AE	Adverse event
Assigned quadrant	Assigned quadrant (ie, left or right buttock, or the left or right posterolateral thigh) that was suitable for treatment and was randomly assigned in the double-blind study (EN3835-201). To be suitable for treatment the quadrant must have an Investigator CR-PCSS and subject PR-PCSS score of 3 or 4 and a Hexsel CSS score of no greater than 13 at Screening B visit and at Day 1 visit.
AUX-I	Clostridial class I collagenase
AUX-II	Clostridial class II collagenase
CFR	Code of Federal Regulations
CRF	Case report form
CR-PCSS	Clinician-Reported Photometric Cellulite Severity Scale
CSS	Cellulite Severity Scale
ECG	Electrocardiogram
eCRF	Electronic case report form
EDC	Electronic data capture
EFP	Edematous fibrosclerotic panniculopathy
FDA	Food and Drug Administration
GCP	Good clinical practice
HREC	Human research ethics committee
IB	Investigator Brochure
ICF	Informed consent form
ICH	International Conference on Harmonisation
IEC	Independent ethics committee
I-GAIS	Investigator Global Aesthetic Improvement Scale
IND	Investigational new drug
IRB	Institutional review board
ITT	Intent-to-treat
kDa	Kilodalton
MedDRA	Medical Dictionary for Regulatory Activities
mITT	Modified intent-to-treat
PCS	Potentially clinically significant
PR-PCSS	Patient-Reported Photometric Cellulite Severity Scale
Qualified designee	Qualified by education and training to perform the study procedure (eg, sub-Investigator, nurse)

Table 5: Abbreviations and Specialist Terms (Continued)

Abbreviation	Definition
SAE	Serious adverse event
SAP	Statistical Analysis Plan
Selected quadrant	Quadrant (ie, left or right buttock, or the left or right posterolateral thigh) that is suitable for treatment and is selected by patient and investigator for treatment. To be suitable for treatment the quadrant must have an Investigator CR-PCSS and subject PR-PCSS score of at least 3 or 4 and a Hexsel CSS score of no greater than 13 at Screening B visit.
S-GAIS	Subject Global Aesthetic Improvement Scale
TEAE	Treatment-emergent adverse event; adverse events that occur on or after the first injection of study drug

8. INTRODUCTION

8.1. Edematous Fibrosclerotic Panniculopathy

Edematous fibrosclerotic panniculopathy (EFP), commonly known as cellulite, has been defined as a local metabolic disorder of subcutaneous tissues that results in an alteration of skin topography.⁽¹⁾ The condition manifests as dimpled skin, described as an orange-peel, cottage cheese, or mattress texture, particularly in the gluteal-femoral region.^(2,3) EFP is caused by herniation of subcutaneous fat lobules through the dermohypodermal junction. This creates an uneven surface with dimpling.⁽¹⁾ EFP is a medical condition resulting in a potentially cosmetically unacceptable alteration of the skin, and affects an estimated 85% to 98% of postpubertal women.^(1,3)

The pathophysiology of EFP is not completely understood, but there are 3 main theories: edema resulting from excessive hydrophilicity of the intercellular matrix, alteration of the regional microcirculation, and different anatomical conformation of collagenous subcutaneous tissues in women versus men.⁽⁴⁾

It is known that EFP is different from generalized obesity. In generalized obesity, adipocytes undergo hypertrophy and hyperplasia that are not limited to the pelvis, thighs, and abdomen.⁽¹⁾ In areas of EFP, adipocytes have physiologic and biochemical properties that differ from adipose tissue located elsewhere. Large, metabolically-stable adipocytes characterize EFP-prone areas; thus, the responsiveness to catecholamine-induced lipolysis is less in EFP tissues compared to visceral fat, which has the greatest responsiveness.⁽¹⁾

Subcutaneous fat lobes are separated from one another by thin, usually rigid strands of collagenous connective tissues, which cross the fatty layers and connect the dermis to the underlying fascia. These septa stabilize the subcutis and divide the fat. In EFP, shortening of the collagen septa due to fibrosis provokes retraction at the insertion points of the trabeculae, causing the depressions that characterize EFP.⁽²⁾ There are a higher percentage of thinner, perpendicular hypodermal septa in women with EFP than in men.⁽¹⁾ Weight gain makes EFP more noticeable, but it may be present even in thin subjects. Genetics may also play a role since EFP tends to run in families.

8.2. Current Edematous Fibrosclerotic Panniculopathy Treatments

There are therapies that have been utilized in an attempt to treat cellulite. Despite multiple therapeutic modalities, there is little scientific evidence that any of these treatments are beneficial. In fact, much of the evidence is anecdotal, subjective, or based only on patient self-assessment.⁽⁵⁾ Some of the historical treatments for EFP have included:

- Weight loss: Weight loss generally decreases the severity of EFP but may only have a variable effect on EFP grades.⁽⁶⁾
- Pharmacological agents (eg, xanthines, retinoids, lactic acid, and herbals): Although there are numerous topical treatments that are available over the counter, there are no well-designed or large-scale studies demonstrating the effectiveness of any of these

therapies.⁽⁵⁾ Additionally, ingredients in some of the topical treatments are unknown and may pose an increased risk for adverse effects.⁽⁵⁾

- Massage: Endermologie or lipomassage kneads the skin between rollers. This type of vigorous massage is posited to increase blood flow and reduce excess fluid in EFP prone areas. In a 12-week, randomized, controlled study of 52 women that examined the effectiveness of either endermologie or aminophylline versus a combination of both, there was no statistical difference in the thigh measurement between subjects.⁽⁷⁾
- Liposuction: Liposuction can reshape the body, but it does not typically correct cellulite as it does not interrupt collagen septae in a directed fashion. Additionally, liposuction is not a recommended treatment for cellulite given the potential for poor cosmetic outcome.^(5,6)
- Mesotherapy: Mesotherapy involves injecting solutions containing various substances, eg, methylxanthines, to dissolve subcutaneous fat; however, this type of therapy often results in unwanted side effects, including infection, urticarial reactions, and bumpy or uneven skin contours.⁽⁶⁾ To date, there are no regulatory approved mesotherapy mixtures for the treatment of EFP.
- Radiofrequency: Radiofrequency systems may temporarily improve the appearance of EFP after a series of treatments; but long-term efficacy has not been demonstrated.⁽⁶⁾
- Subcision: Subcision is an invasive surgical technique that severs the septa holding fat lobules that cause the skin dimpling associated with EFP. In a study conducted by Hexsel and Mazzucco, 232 subjects had subcision for the treatment of EFP.⁽⁸⁾ Although 78% of subjects were satisfied after 1 treatment, there were no objective criteria by which to assess improvement, thereby limiting the value of this study. Additionally, side effects reported in this study included pain, bruising for 3 to 6 months, hyperpigmentation for 2 to 10 months, and skin puckering.^(5,6) These effects are most likely due to the trauma from shearing the septa with a large gauge needle (eg, 16 or 18 gauge) or other cutting devices.
- Powered subcision: Powered subcision is a surgical technique utilizing a powered needle apparatus to sever the septa holding fat lobules that cause skin dimpling associated with EFP. The Cellfina® powered subcision device was recently approved by Food and Drug Administration (FDA; 2015) for the treatment of cellulite.
- Laser: Intense pulsed light has been investigated for the treatment of cellulite. Triactive® is an FDA-approved low-fluorescence 810-nm light source combined with a 915-nm laser. In a study of 16 female subjects who underwent 12 treatments with the Triactive, 21% had improvement (based on 5 blinded Investigators' analysis of photographs with respect to appearance of cellulite, skin tone, and texture) of their cellulite.⁽⁹⁾ The CelluLaze™ system was used to treat cellulite on the thighs of 10 healthy women.⁽¹⁰⁾ In this Investigator-initiated study, subjects received a single treatment with a 1440-nm laser. During the CelluLaze procedure, which is performed under a local tumescent and general anesthetic, the physician inserts a small cannula through the skin and the device technology directs controlled, laser thermal energy to

the treatment zones. The laser is designed to diminish the lumpy pockets of fat by melting the hypodermal fat; release the areas of skin depression through thermal subcision of the septal tissue; and increase the elasticity and thickness of the skin by melting the fat in the dermal invaginations. Subjective physician and subject evaluations indicated improvement in the appearance of cellulite and high patient satisfaction that persisted for a year. For both the Triactive and CelluLaze studies, there were no control groups and significance was not tested.

There remains an unmet medical need for safe and effective nonsurgical therapies to improve the esthetic outcome in women with cellulite. To effectively treat cellulite, a therapeutic approach may require disruption of the dermal septa, which are composed of collagen and cause the skin dimpling which is bothersome to many women.

